3.6 Description of Variables

3.6.1 Description of Outcome Variables

Table 1 describes the outcome variables and data sources.

Table 1. Outcome variables and sources

Outcome	Endpoint	Data Source
Primary Outcomes		
Depression	Difference in changes of the summed score on the Center for Epidemiologic Studies Depression Scale (CES-D) between baseline and 12 months.	Baseline and 12-month interviews
Resilience	Difference in changes of the summer score on the Connor-Davidson Resilience Scale-25 (CD-RISC 25)	Baseline and 12-month interviews
Social Support	Difference in changes of the summer score on the Social Support Scale (MOS-SSS)	Baseline and 12-month interviews
Secondary Outcomes		
Stress	(a) Difference in changes of the summer score on the Social Support Scale (MOS-SSS) (b) Change (either direction) of hair cortisol levels	(a) Baseline and 12-month interviews (b) Baseline and 12-month hair sample
Knowledge and Empowerment	Subscale summed scores on the Trauma Informed Practice Scale (TIPS)	12-month interview (Tertulias group only)
Social Network Analysis		1-month interview

3.6.2 Description of Other Measures

Table 2 lists other outcomes, covariates, potential mediators and moderators.

Table 2. Description of other potential covariates

Variable	Data Source	Data Type
Sociodemographics		
• Age	Baseline	Continuous
• Race	Eligibility Screener	Categorical
• Marital status	Baseline Interview	Categorical
• Income	Baseline Interview	Continuous
• Education	Baseline Interview	Categorical
• Speaks English	Baseline Interview	Categorical
• Access to internet	Baseline Interview	Categorical
• Access to a computer	Baseline Interview	Categorical
• Family in Albuquerque	Baseline Interview	Categorical
• Know neighbor's name	Baseline Interview	Categorical

Table 2. Description of other potential covariates

Variable	Data Source	Data Type
• Interaction with family in Mexico	Baseline Interview	Categorical

4 Sample Size

We will recruit a total of 240 participants through our two partner agencies that both have a large clientele with our target population. Sample size estimates accommodate 33% attrition. With the expectation that 100 participants will complete the study in each arm, the following minimum hypothesized changes in outcome measures will be detected with >80% power, assuming type I error $\alpha = 0.017$ for three primary outcome measures (one in each Aim):

1. An 8-point decrease in depression as measured by the CES-D for the Intervention arm, from baseline to 12 months, with at least a 6.5-point greater decrease than control participants (between arms effect size Cohen's $d = 0.43$ with $SD = 15$), as shown to be feasible in prior work.^{11,12}
2. Cohen's d effect size ≥ 0.33 comparing arms on the changes over time of the CD-RISC scores, indicating increased resiliency in the intervention arm as compared to the control arm.¹³⁻¹⁵
3. Decreased social isolation as measured by the MOS-SSS in the intervention arm as compared to the control arm over time with Cohen's $d \geq 0.5$ ($SD = 16$).¹⁶⁻¹⁸

5 General Analysis Considerations

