## PROTOCOL TITLE: TERTULIAS

### 1.0 Objectives

The purpose of this project is to test TERTULIAS (Spanish for “conversational gatherings”), an innovative peer support group model for reducing social isolation and depression among female Mexican immigrants (FМИs).

TERTULIAS is a peer support group model with bi-directional knowledge exchange with a trained facilitator and culturally appropriate food sharing and storytelling.

**Goal:** We will conduct a randomized controlled trial with 240 female FМИs. Intervention participants will attend a weekly peer group session over 12 months. Control group participants will receive a bimonthly check-in call. All will be surveyed using validated instruments and give hair samples gathered at baseline and 12 months. A subset will be interviewed, and group sessions will be documented. We will triangulate data gathered using different methods with a **QUAL→QUAN** simultaneous data collection and analysis approach to integrate, converge, and elaborate findings in a way that would not be feasible using only one method. Our prior work and demonstrated capacity to work with a hard-to-reach population will make this project a success.

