### 4.0 Study-Wide Number of Subjects

**Sample Size.** We will recruit 252 participants (N=252). **We will randomize participants into one of two arms.** We will enroll 60 participants each year during Y1 and Y2 (30 Arm 1 and 30 Arm 2). During Y3 and Y4, we will increase enrollment to 66 each year (33 Arm 1 and 33 Arm 2) to ensure we account for attrition to be able to power the study. Sample size accommodates attrition.

■) Arm 1 (n=126): Control participants will be recruited in four 12-month cohorts to coincide with the intervention cohorts. At the end of their 12-month participation in the control group, they will be offered the option of participating in the Y2, Y3, or Y4 intervention cohort or if they prefer, to join the ongoing group at the Hopkins Center outside of the research.

■) Arm 2 (n=126): Intervention participants will be recruited in four 12-month cohorts. Each cohort will be divided into three groups. With 3 groups in each cohort, over the four cohort cycles, we will have a total of 12 groups.

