OFFICIAL GRANT TITLE	Addressing Social Isolation to Reduce Depression Among Women of Mexican Origin
STUDY TITLE	Tertulias
NCT IDENTIFIED NUMBER	NCT04254198
FUNDED BY	National Institute on Minority Health and Health Disparities
GRANT NUMBER	5R01MD014153-05
SAP VERSION	1.0
SAP VERSION DATE	June 23, 2024
TRIAL STATISTICIAN	[name]
PROTOCOL VERSION (SAP associated with)	1.0
TRIAL PRINCIPAL INVESTIGATORS	[name]
SAP AUTHOR(s)	[name]

TABLE OF CONTENTS

1	INTRODUCTION.....	4
2	STUDY AIMS AND ENDPOINTS	4
2.1	Study Aims	4
2.2	Outcomes	4
3	STUDY METHODS.....	4
3.1	General Study Design and Plan.....	4
3.2	Intervention Arms	5
3.3	Study Population	5
3.4	Randomization and Blinding	6
3.5	Study Assessments.....	6
3.6	Description of Variables.....	7
4	SAMPLE SIZE	8
5	GENERAL ANALYSIS CONSIDERATIONS.....	8
5.1	Timing of Analyses	8
5.2	Analysis Populations.....	8
5.3	Covariates and Subgroups	8
5.4	Missing Data.....	8
5.5	Summary of Study Data	9
5.6	Subject Disposition	9
5.7	Protocol Deviations	9
5.8	Outcome Analyses.....	9
5.9	Baseline Descriptive Analyses	9
5.10	Primary Outcome Analysis.....	9
5.11	Secondary Outcome Analyses.....	10
5.12	Exploratory Outcome Analyses	11
5.13	Sub-Group Analyses.....	11
5.14	Post-Hoc Analyses.....	11

5.15	Safety Analyses.....	11
6	REFERENCES.....	13

1 Introduction

We will conduct a randomized controlled trial of “Tertulias,” an innovative social isolation peer support group model, with 240 women of Mexican origin to contribute to the science of a holistic, multi-level (individual, family, and group) intervention to reduce health disparities related to social isolation and depression among this population. Our transdisciplinary team will use a rigorous, mixed-methods, community-engaged approach that includes a cutting-edge biological assessment of hair cortisol as a biomarker for chronic stress.

2 Study Aims and Endpoints

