3.2.2 Arm 2: Intervention

We will conduct Tertulias structured dialogue groups using the model we developed and tested through our preliminary research (see [name] et al. 2021).⁹ Each group will have approximately 10 women and will meet weekly for 2 hours over a 12-month period. Group meetings will be conducted in Spanish, led by a team of two FMI facilitators using our structured dialogue approach. Because of required safety restrictions related to the COVID-19 pandemic, our original intention to hold these groups in-person was amended to hold the groups remotely by Zoom. We will work further with each Arm 2 participant to ensure that they know how to use Zoom and have electronic access.

[figure not shown]

Figure 1. CONSORT diagram for the Tertulias study.

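### SAP section 4: 240 recruits, 33% attrition and 100 completers per arm cannot all hold, and the documents state three different totals

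*SAP*

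**What the plan says.** SAP section 4 makes three statements in succession: "We will recruit a total of 240 participants through our two partner agencies"; then "Sample size estimates accommodate 33% attrition"; then "With the expectation that 100 participants will complete the study in each arm". The last opens a claim of more than 80% power for each of three primary outcomes at a type I error of 0.017.

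The protocol relies on the same 100 completers per arm in its power statements for Aims 1, 2 and 3 (section 11.0). It gives no attrition rate; section 4.0 says only "Sample size accommodates attrition", and section 22.0 repeats this.

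The total to be recruited varies:

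- **240:** Protocol 1.0 ("We will conduct a randomized controlled trial with 240 female"), SAP section 1 ("with 240 women of Mexican origin") and SAP section 4.
- **252:** Protocol 4.0 ("We will recruit 252 participants (N=252"), 21.0 and 22.0.
- **260:** Protocol 5.0.
- **136 per arm:** Protocol 22.0, beside its own total of 252.

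**The concern.** The three figures in SAP section 4 are tied by one identity: completers equal recruits times one minus attrition. They do not satisfy it. A reader is told that the trial can lose a third of its participants and still have 100 per arm for the primary analyses, which is untrue for every total in the documents.

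Nor can the reader tell which figure to correct. The 33% appears only in SAP section 4. The 100 per arm supports the power claims in both documents. Two of the totals each have a design rationale behind them. The final report will need one planned total, one attrition allowance and one completer target against which the observed disposition can be judged.

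**Working it through.** **Inputs.** Total 240, attrition 33% and 100 completers per arm (SAP section 4). Alternative totals 252 and 260, and the 272 implied by 136 per arm (Protocol 4.0, 5.0, 21.0, 22.0). Allocation 50:50 (Protocol 5.0 and 21.0, Randomization). Alpha 0.017 per primary outcome; sidedness is not stated. Effect sizes: CES-D 6.5/15 = 0.433, CD-RISC 0.33, MOS-SSS 0.5 (SAP section 4).

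**Step 1: try to reproduce the plan's figure.** Completers per arm = (N/2) × (1 − 0.33). For N = 240: 120 × 0.67 = 80.4, not 100. In the other direction, 100/0.67 = 149.3, so 150 per arm or 300 in all. The common slip of multiplying by 1.33 gives 200 × 1.33 = 266. Neither gives 240.

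**Step 2: every total in the documents.** Maximum loss that keeps 100 per arm = 1 − 200/N.

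| Total | Per arm | Completers per arm at 33% loss | Maximum loss leaving 100 per arm |
|---|---|---|---|
| 240 | 120 | 80.4 | 16.7% |
| 252 | 126 | 84.4 | 20.6% |
| 260 | 130 | 87.1 | 23.1% |
| 272 (from 136 per arm) | 136 | 91.1 | 26.5% |

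No row gives 100 at 33%.

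**Step 3: which total?**

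- For 240: 12 groups (Protocol 4.0) of 10 women (Protocol 21.0) make 120 intervention participants, so 240 in all.
- For 252: the yearly plan in Protocol 4.0 and 22.0 is 60 + 60 + 66 + 66 = 252, or 30 + 30 + 33 + 33 = 126 per arm. Over 12 groups that is 126/12 = 10.5 per group, which fits SAP 3.2.2: "Each group will have approximately 10 women".
- For 260: no cohort or group plan supports it.
- For 136 per arm: 2 × 136 = 272 contradicts both the total and the yearly plan printed in the same section.

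**Step 4: effect on power.** Assumed test: unadjusted two-sample t test on change scores, no clustering or covariate adjustment, noncentrality d√(n/2), 2n − 2 degrees of freedom, alpha 0.017. Cells show two-sided / one-sided power.

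| Completers per arm | CES-D | CD-RISC | MOS-SSS |
|---|---|---|---|
| 100 | 74.4% / 82.3% | 47.2% / 57.9% | 86.9% / 91.9% |
| 87 | 67.3% / 76.4% | 41.0% / 51.7% | 81.2% / 87.6% |
| 84 | 65.4% / 74.8% | 39.5% / 50.2% | 79.6% / 86.4% |
| 80 | 62.9% / 72.6% | 37.5% / 48.1% | 77.2% / 84.6% |

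The protocol's figure of more than 86% for MOS-SSS at 100 per arm is met by both versions, so it does not settle sidedness.

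**The case against.** The strongest defence is that the 33% and the 100 describe different scenarios: 33% as the worst loss the design could bear, 100 per arm as the expected result. There is a numerical hint of this. By the normal approximation, d = 0.5 at two-sided alpha 0.017 and 80% power needs 84 per arm, and 84/0.67 = 125.4, or 126 per arm after rounding up, which is 252 in all. But neither document states this derivation. It uses 252 where the SAP says 240, and it serves MOS-SSS only. At 80 or 84 per arm CES-D power is about 63% to 65% two-sided and 73% to 75% one-sided, against a claim of more than 80%. So this reading does not rescue the section.

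A second objection is that nothing in the conduct or analysis depends on the 33%. That stands. The last cohort was to be consented in summer 2023 (Protocol 26.0), and the SAP is dated June 23, 2024. The outcomes, mixed model, alpha and intervals make no use of the attrition figure. The point concerns the reported justification only.

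A third is that back-calculating 16.7% or 20.6% presents a residual as a planning assumption. This is fair as a caution about wording. The figure is the largest loss compatible with 100 per arm, which is what accommodating attrition means, and it should be labelled that way.

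**Conclusion.** The concern holds. SAP section 4 is wrong as written: at 33% attrition the completers are about 80 per arm from 240, 84 from 252 or 87 from 260, not 100. The stated tolerance is 1.4 to 2 times what 100 per arm allows (33/23.1 to 33/16.7). This part rests only on equal allocation.

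The effect on power is modest for MOS-SSS and depends on sidedness: two-sided it falls from 87% to 79.6% at 84 or 77% at 80, while one-sided it stays above 80%. For CES-D, the only support for the 80% claim at 100 per arm is the one-sided reading (82%), and that too is lost at 87 or fewer. All power figures assume the unadjusted t test above, and the planned mixed model may differ.

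The documents do not show which figure is in error. The shortfall for CES-D and CD-RISC that already exists at 100 per arm (74% and 47% two-sided, 82% and 58% one-sided) is a separate matter.

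**What to change.** Reconcile the total, the attrition rate and the completers in SAP section 4, and show the calculation, from the source calculation if it can be found.

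- **If 100 completers per arm is kept:** replace 33% with 20.6% (1 − 200/252) or 16.7% (1 − 200/240), described as the maximum loss compatible with 100 per arm. The power sentences need no change on this account.
- **If 33% is kept:** replace 100 with 84 per arm (total 252) or 80 (total 240) in SAP section 4 and in Protocol 11.0, Aims 1 to 3. Restate power in both documents at that number, naming the test and its sidedness. Under the two-sided assumptions above, CES-D, CD-RISC and MOS-SSS have 65%, 39.5% and 79.6% at 84 per arm, and 63%, 37.5% and 77% at 80.

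Either way:

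- Use the chosen total in Protocol 1.0, 4.0, 5.0, 21.0 and 22.0 and in SAP sections 1 and 4.
- Correct 136 per arm in Protocol 22.0 to 126 (if 252) or 120 (if 240).
- If 252, describe the group size in Protocol 21.0 as approximate, as the SAP does. If 240, reconcile the plan to enrol 66 a year in Protocol 4.0 and 22.0.
- If CES-D and CD-RISC power is restated in SAP section 4, restate Aims 1 and 2 of Protocol 11.0 at the same time.

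The cost is wording only. The price is a less favourable statement: a lower attrition tolerance in the first case, fewer completers and lower power in the second. No recruitment is added and no analysis changes.

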#### **Aim 2. To test whether an intervention using a “women’s funds of knowledge” approach results in improved resilience, knowledge and empowerment.**

**Question:** Does an intervention design that encourages participants to share knowledge they developed through life experience and that values this knowledge as a form of expertise nurture protective factors (resilience and knowledge/empowerment) to help FМИs adapt to the immigration context and disrupt the mechanisms that produce health disparities?

**Hypothesis:** Incorporating, valuing and validating women’s knowledge and experience in the design of a peer support group intervention will improve participant capacity to adapt to the immigrant context and provide participants with empowering knowledge to deal with new situations. Intervention participants will have higher scores at 12 months and have a larger increase over time as compared to controls ( $d = 0.5$ ) on the Connor-Davidson Resilience Scale-25 (CD-RISC 25). We will assess knowledge and empowerment at 12 months and expect to find high scores with the Trauma-Informed Practice (TIP) Scale (which is designed for post-use).

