**Aim 2.** To test whether an intervention using a “women’s funds of knowledge” approach results in improved resilience, knowledge and empowerment. ***Primary Hypothesis:*** Intervention participants will have higher scores at study completion and have a larger increase over time as compared to controls on the Connor-Davidson Resilience Scale-25 (CD-RISC 25). Based on previous literature, we expect to find a moderate effect size ( $d = 0.5$ ) of the change scores between arms, favoring the intervention arm. **Power and Sample Size:** Based on standard deviations of CD-RISC scores reported in the literature for changes over time reported when comparing two arms ( $SD = 1.0-9.2$ ), with 100 participants per arm completing both time points, we can detect a Cohen's  $d$  effect size  $\geq 0.33$  with 80% power and type I error = 0.017. The range of effect sizes for differences between arms previously reported range from 0.32 to 7.4. ***Secondary Descriptive Measure:*** To assess knowledge and empowerment in the intervention arm only, we will calculate summary statistics for the six subscales of the Trauma-Informed Practice (TIP) Scale administered post intervention at 12 months, and an overall total score. Means and 95% CIs for the total and subscales will be reported.

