## PROTOCOL TITLE: TERTULIAS

**Aim 3.** To investigate whether a culturally situated peer group intervention using a women's funds of knowledge approach can give participants' a sense and experience of social and physical connection ("emplacement") that is lost in the process of immigration. **Primary Hypothesis:** The experimental participants will have a marked increase in social support scores than the control group using the MOS SSS (expect  $d \geq 0.5$ ). A limited number of previous studies assessed changes over time between arms and reported that interventions have variable effects on social isolation, with effect sizes ranging from small ( $d = 0.2$ ) to very large ( $d = 1.5$ ). **Power and Sample Size:** Given our previous work where we qualitatively observed extremely positive changes in perceived social isolation, our sample size (100 participants per arm) will provide >86% power to detect differences between arms in change scores from baseline to 12 months on the MOS SSS with effect sizes as small as  $d = 0.5$  (type I error = 0.017). **Secondary Measure:** Social connectedness will be measured using **Social network analysis (SNA)**. Led by Co-I [name], our SNA will involve three types of analyses: 1.) Using answers to questions modeled after the General Social Survey, an individual social network will be constructed for each participant. Baseline and post-survey individual networks will be compared and changes in network density and characteristics (e.g., family, friends, locality, distance) will be assessed. 2.) The level of inclusion of *other* study participants in individual social networks pre- and post-intervention will be assessed. Combining the individual networks of participants in each intervention group will constitute what is referred to as a "complete network." Complete networks can be analyzed using network-level measures--centrality, betweenness, and degree--to identify internal social dynamics of the intervention groups. 3.) Using questions about local resources (e.g., the health insurance exchange, health navigation programs, local subsidized food coop programs, public food and benefit programs such as SNAP or WIC, free legal assistance programs, low-cost ESL and GED programs, domestic violence programs, local food charities, local clothing charities, transportation and utilities assistance programs, etc.), we will assess changes in each study participant's awareness of, knowledge about, and likelihood of accessing resources.

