5.10 Primary Outcome Analysis

5.10.1 Primary Hypotheses

5.10.1.1 Primary Hypothesis 1

We hypothesize that the Tertulias arm will have at least an 8-point decrease in depression as measured by the CES-D, from baseline to 12 months, with at least a 6.5-point greater decrease

than control participants (between arms effect size Cohen's $d = 0.43$ with SD = 15)

5.10.1.2 Primary Hypothesis 2

We hypothesize that the Tertulias arm will increase their resilience more than the control arm, from baseline to 12 months, by a Cohen's d effect size ≥ 0.33 .

5.10.1.3 Primary Hypothesis 3

We hypothesize that the Tertulias arm will decrease their social isolation more than the control arm, from baseline to 12 months, as measured by the MOS-SS with Cohen's $d \geq 0.5$.

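### CD-RISC power at d = 0.33 is about 47% two-sided (58% one-sided), not the stated 80%; the CES-D power claim cannot be verified as written

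*SAP*

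**What the plan says.** SAP section 4 expects 100 completers per arm, sets type I error at 0.017 for each of three primary outcomes, and states that "the following minimum hypothesized changes in outcome measures will be detected with >80% power". Its second item is a Cohen's d of at least 0.33 "comparing arms on the changes over time of the CD-RISC scores". SAP 5.10.1.2 carries that threshold into Primary Hypothesis 2: "We hypothesize that the Tertulias arm will increase their resilience more than the control arm", by d of at least 0.33.

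The Protocol's Aim 2 power paragraph (section 11.0, Statistical Analysis of Survey Responses) says that "with 100 participants per arm completing both time points, we can detect" d of 0.33 or more with 80% power at type I error 0.017. It describes the basis as follows: "Based on standard deviations of CD-RISC scores reported in the literature for changes over time reported when comparing two arms". The effect the Protocol actually hypothesises is larger. In that same section "we expect to find a moderate effect size" of d = 0.5 for the change scores between arms, and section 1.0, Aim 2 says "Intervention participants will have higher scores at 12 months and have a larger increase over time as compared to controls", again with d = 0.5.

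For Aim 3 (MOS SSS), with the same n and alpha, the Protocol claims ">86% power to detect differences between arms in change scores" at d = 0.5. For CES-D, both documents give a 6.5-point between-arm difference, SD 15 and d = 0.43, with power above 80%. Neither document states the sidedness of the power calculations or whether the CES-D SD of 15 belongs to the score or to its change.

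**The concern.** With the same n, alpha and kind of contrast, the power stated for CD-RISC at d = 0.33 (80%) is close to that stated for MOS SSS at d = 0.5 (above 86%). Those two figures fit together badly, and a direct calculation shows that the CD-RISC one is wrong.

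CD-RISC is one of three primary outcomes. If the true effect is 0.33, the chance of missing it is about 53% two-sided, where the plan implies at most 20%. A reader who trusts the stated power would take a non-significant CD-RISC result as stronger evidence of no effect than it is. A null result is a realistic prospect: Protocol section 9.0 (Additional Survey Questions) reports that a preliminary analysis at the end of Year 2 found little or no difference between arms on the survey measures, although it does not name CD-RISC. For the arm contrast, SAP 5.10.2 lists only a coefficient, standard error and p-value, so readers may lean on the power statement.

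**Working it through.** **Inputs.** n = 100 completers per arm and alpha = 0.017 (SAP section 4; Protocol Aims 1 to 3). CD-RISC d = 0.33 on change scores (SAP section 4; Protocol Aim 2). MOS SSS d = 0.5 (Protocol Aim 3). CES-D d = 6.5/15 = 0.433 (SAP section 4; Protocol Aim 1).

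**Formula.** Two-sample t test on change scores: noncentrality = d × √(n/2), df = 2n − 2. At n = 100, √50 = 7.071 and df = 198. The critical value is 2.407 two-sided and 2.135 one-sided. With two time points and complete data, the time-by-arm interaction in SAP 5.10.2 is this same contrast. The listed covariates are baseline characteristics and do not include the baseline outcome. In one simulated data set the interaction SE was 0.1515 from the mixed model, with or without two baseline covariates, and from the t test.

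**A figure that reproduces.** MOS SSS: 0.5 × 7.071 = 3.536, giving 86.9% two-sided and 91.9% one-sided. The Protocol's figure of above 86% lies next to the two-sided value.

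**The CD-RISC figure.** 0.33 × 7.071 = 2.333, which is below the two-sided critical value of 2.407, so two-sided power must be under one half.

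| Setting, d = 0.33 | Two-sided | One-sided |
|---|---|---|
| 100 per arm, alpha 0.017 (as stated) | 47.2% | 57.9% |
| 126 per arm (Protocol 4.0), alpha 0.017 | 58.6% | 68.7% |
| 136 per arm (Protocol 22.0), alpha 0.017 | 62.6% | 72.2% |
| 100 per arm, alpha 0.05 | 64.1% | 75.2% |

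A simulation of 60,000 trials at 100 per arm and alpha 0.017 gave 47.2% and 58.0%. The smallest d with 80% power at 100 per arm is 0.460 two-sided and 0.421 one-sided.

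**Possible source of the 80%.** A one-sample or paired test with n = 100 has noncentrality 0.33 × √100 = 3.30, critical value 2.428 and power 80.7% two-sided. That matches the stated figure, but it describes a within-arm change. It suggests, without proving, that a within-arm formula was used for a between-arm contrast.

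**Consistency of Aims 2 and 3.** If d = 0.33 had 80% power, d = 0.5 would have about 99%. If d = 0.5 has 86%, d = 0.33 has 46% two-sided or 50% one-sided. Since above 86% formally includes 99%, this is a sign of inconsistency and not proof.

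**CES-D.** If SD 15 is the SD of change, power is 73.6% (d = 0.43) to 74.4% (d = 0.433) two-sided, and 81.7% to 82.3% one-sided. If SD 15 is a raw-score SD, the SD of change is 15 × √(2(1 − r)) for a baseline-to-12-month correlation r, which the documents do not give. Two-sided power is then 57% at an assumed r of 0.3, 74% at 0.5, 80% at 0.56 and 84% at 0.6.

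**Clustering.** The intervention arm meets in groups of about 10 and no ICC is given. With 12 groups there are 100/12 = 8.3 completers per group. Inflating the variance in that arm only by 1 + (8.3 − 1) × ICC, two-sided power for d = 0.33 is 45.6% at an assumed ICC of 0.01, 39.9% at 0.05 and 34.3% at 0.10.

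**The case against.** - **The d might be scaled on the raw-score SD.** Reaching 80% would then need a correlation of 0.74 two-sided or 0.69 one-sided. The Protocol bases its figure on SDs of change and the SAP compares arms on change, so the text does not support this reading.
- **The mixed model might gain precision.** If baseline means were constrained equal across arms, two-sided power for d = 0.33 would be about 69%, 61% and 55% at assumed correlations of 0.3, 0.5 and 0.7, and CES-D with SD 15 as the SD of change would reach 87% at 0.5. SAP 5.10.2 specifies no such constraint, and CD-RISC still misses 80% at these correlations. It does mean that 47% is not a ceiling and that the CES-D figure depends on the model.
- **The effect actually expected is adequately powered.** This stands for the Protocol's d = 0.5, with 87% two-sided. The 53% miss rate applies at a true effect of exactly 0.33, while the SAP says at least 0.33. But 0.33 is the minimum effect for which the SAP claims the power.
- **A reader can judge a null from an interval.** Partly true: Protocol section 11.0 plans a 95% interval for the arm difference, and one can be built from the SAP's coefficient and standard error. That limits the harm but does not make the power figure right.
- **One hundred completers is itself in doubt.** SAP section 4 recruits 240 and allows 33% attrition: 240 × 0.67 = 160.8, or about 80 per arm. At 80 per arm, two-sided power is 37.5% for d = 0.33 and 77% for d = 0.5. This stands, and it makes the CD-RISC figure worse.

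**Conclusion.** The concern holds. The CD-RISC power statement is wrong in both documents: at 100 completers per arm, alpha 0.017 and d = 0.33 on change scores, power is 47% two-sided or 58% one-sided against the stated 80%, a shortfall of 22 to 33 percentage points. The conclusion does not depend on sidedness, on which recruitment total is used, or on the multiplicity adjustment. The exact figures assume independent participants and an unconstrained time-by-arm interaction. Clustering within groups would lower them; a baseline constraint would raise them.

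The CES-D claim is unspecified, not shown to be wrong. The 98.3% intervals in SAP 5.10.2 (100 − 1.7 = 98.3) and the Aim 3 figure both point to two-sided testing. On that reading, with SD 15 as the SD of change, CES-D power is about 74% and falls short of the claim. This part is a request for clarification, and the case for correction rests on CD-RISC alone.

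**What to change.** 1. In SAP section 4 and Protocol Aim 2, replace the CD-RISC power statement with: *With 100 completers per arm and two-sided alpha 0.017, power is about 47% for d = 0.33 and 87% for d = 0.5; the smallest effect detectable with 80% power is d = 0.46, assuming independent participants.* If the test is meant to be one-sided, say so and use 58%, 92% and 0.42. Check the 100 completers against the 33% attrition allowance at the same time.
2. Reconcile SAP Primary Hypothesis 2 (0.33) with the Protocol hypothesis (0.5). Because arm-level survey results were examined at the end of Year 2, date the change and record that it followed that look.
3. In SAP section 4 and Protocol Aim 1, state the sidedness and whether SD 15 is the SD of change. If it is two-sided and the SD of change, restate CES-D power as about 74%.

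The cost is wording. No test, estimate or sample size changes and no extra participants are proposed, though item 2 does alter a stated hypothesis. The downside is that the stated power becomes less favourable.
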